10.3.2 Informed Consent and Assent

All study team staff are trained to guide participants through the consent/assent process.

Preliminarily eligible subjects will be contacted via phone and/or email for informed consent and assent. The informed consent process will be conducted following all federal and institutional regulations relating to informed consent. Informed consent will be obtained prior to conducting any study-related activities. After families respond to the email recruitment script and express interest in participating in our study, we will send the consent form via email for them to review and follow up with a phone call. During the phone call, trained study personnel will explain the study and complete pre-screening. Participants, under the age of 18 and 18-21 without the capacity to consent will then be asked if they would like to discuss the assent form at this time and be invited to a video session or schedule a separate session. The Teach Back practice will be used to obtain informed consent/assent and confirm their understanding. Participants are welcome to complete the consent/assent at the time of review with trained study personnel or take their time to think about participation before completing the form. This consent form must be signed by one parent/legal guardian. We will require only one parental/legal guardian signature for consent due to the minimal risk of this study. If the participant is between 18-21 and does not have the capacity to consent, an LAR will sign the consent form. Assent will be obtained from all participants who lack the capacity to consent (8-17 year-olds and adults 18-21 lacking consent capacity). The study procedures will be explained to the participant in an understandable way and the participant's assent will then be requested. Only participants who can provide affirmative agreement that they wish to participate will be included. The consent form has a signature block to document the participant's assent. If the child is over 18 years old and has the capacity to give consent, they must sign the consent form themselves in addition to their parent as they both are involved in the study as an adult child/parent dyad. Neither children nor adults will be required to provide justification if they do not wish to participate. This will facilitate refusal to participate due to reasons that the child does not wish to disclose (e.g. possible pregnancy) Abbreviated IDE requirements apply for Non-Significant Risk Device. Individuals who are 18-21 that lack the capacity to consent will not be able to participate in the optional MRI study.

10.3.3 Adults with Impaired Decision-Making Capacity

Before enrolling potential participants aged between 18-21, we will evaluate whether they have the ability to provide informed consent. To assess their capacity to consent, we will utilize the teach-back method to ensure they understand the research's purpose, potential risks, absence of direct benefit,

and voluntary nature of participation. If the evaluation confirms their consent capacity, they will be asked to provide consent to participate in the study, unless guardianship requires the guardian's consent. We will adhere to HRP-013 and consult the Office of Legal Affairs to determine the appropriate Legal Authorized Representative (LAR) for individuals deemed to lack consent capacity, as well as any legal queries regarding consent. We will obtain assent from all participants who lack the capacity to consent, and we will describe the study processes in simple language using the teach-back method. Only those participants who give affirmative agreement to participate will be included in the study.

Video sessions will be conducted via HIPAA-compliant WebEx version, secure Zoom, or Microsoft Teams available to UW researchers. In case of remote consent, a 21 Code of Federal Regulations (CFR) Part 11 compliant version of DocuSign, provided by UW, will be used. The authorized member of the research team who obtained consent/assents will sign the form. Printed signed forms will be kept in a locked cabinet in the lab's office, which is only accessible to certain study team members.

Following enrollment, the research team will consistently communicate with the parent/child team during study interactions to confirm their understanding and comfort with the procedures. Specific questions asked by the parent/legal guardian or child will be documented to assist us with determining how best to support their understanding.

10.3.4 Enrollment

A research subject will be defined as "enrolled" in the study when they meet the following criteria:

- The subject has been consented and assented by study staff.
- The subject and study staff have completed all screening documentation.
- The PI has verified that the subject meets all of the inclusion criteria.
- The PI has verified that subject meets none of the exclusion criteria.

10.3.5 Screen Failure and Re-enrollment

A screen failure will occur if, after review of the medical records, the caregiver/child do not fit the criteria to participate. In that case, enrollment will not take place and the study team will discuss the findings with the family/caregivers. No re-enrollment will be considered due to age range and inclusion criteria.

10.3.6 Optional MRI Screening

If subjects meet all other enrollment criteria and confirm interest in being a part of the study, but their medical records do not include radiological confirmation of brain bleed or stroke, we will offer them an MRI screening visit. This MRI will be paid for by research funds and will be consented separately as an optional screening visit. Separate consent is preferable, given that the findings of the MRI will determine if subjects can enroll in the main study. The consent/assent process follow the procedure detailed on 10.3.2.

The potential participant will be provided with a link to a walk through guide of how an MRI is completed at the Waisman Center: (<https://pnl.waisman.wisc.edu/tests-and-interventions/>), or (https://www.youtube.com/watch?v=jFxO_XGp3UM&t=2s). The potential participant will also be provided with a link to listen to what an MRI scan may sound like, such as: (https://www.youtube.com/watch?v=S4DHUlm_Lc8). In addition, if the subject is particularly anxious, s/he will be offered an additional mock scan. At the Waisman Center, the mock scanning room has been designed to very closely enact a neuroimaging procedure with the exception that the scanning apparatus is not capable of generating a magnetic field. Importantly, it also allows for a practice session prior to data collection. The participants will hear an audio file that replicates the scanner noise that occurs during the real scanning session. Study personnel will support and coach subjects if they have any difficulties accommodating to the scanner environment. During this mock practice session the

importance of keeping the head still during the scan is emphasized, and participants have a chance to practice this. These methods have been standard child MRI scans and work well with children.

After completion of an MRI safety screening form, participants will receive an MRI scan at the Waisman Center for Brain Imaging ([name]) or at WISPIIC ([name]). The parent/legal guardian may be permitted to be in the scanning control room during the session, after completing a safety screening, in accordance with facility policy.

Scanning Protocol: The MRI will be done using a 3 Tesla Discovery MR750 MRI scanner (GE Healthcare, Waukesha, WI). Our imaging protocol includes structural imaging and diffusion MRI. The exact scan length and parameters of each scan type (T1, T2, DWI) will be set for this study in coordination with the Waisman Brain Imaging Core staff and the UW radiology team to optimize the quality of data for purposes of determining study eligibility. All of the imaging methods have been previously implemented at UW-Madison. Each sequence will take approximately 5-10 minutes and the total scan time will be approximately 60 minutes.

- Structural Imaging
 - T1-weighted: Anatomical T1-weighted imaging will be obtained using techniques the custom MPnRAGE sequence^(25,26), which inherently removes the intensity variations from inhomogeneities in the coil sensitivities and motion artifacts. This technique has been widely utilized across imaging studies at the Waisman Center, including infant and pediatric populations. The T1-weighted scan will be used in the analysis pipeline to confirm lesion location.
 - T2-weighted: T2-weighted images will be acquired using GE's 3-dimensional CUBE sequence, allowing for high resolution T2-weighted images.
- Diffusion Weighted Imaging: DWI uses extra gradients applied after excitation and before data sampling to encode information about small displacements of water. The strength, direction, and timing of the gradients (called b-value) determine sensitivity of diffusion. A multiple b-value dataset will be acquired, with the number and strength of the b-values and gradient directions optimized for the age range of infants studied. Diffusion imaging data will be acquired with reverse phase encoding schemes in order to correct for susceptibility distortions. Multiband imaging (factor=3) will be used to make the acquisition faster.

A neuroradiologist will review the scan and produce a radiological report to be reviewed by the study medical director who will ultimately determine eligibility. At the request of the subject and caregiver, the medical director will meet also with the subject and their parent to discuss the results of the radiological report within 30 days if the recommendation of the radiologist is to further investigate the unusual results of the images with the participant's own physician. Study teams will not inform subjects of their eligibility until after the results have been communicated by the medical director to the subject and their caregiver or they have declined this discussion.

- "Souvenir" Radiology Images: If an MRI scan was completed with a participant, per IRB policy a three-view research radiology souvenir will be offered for families. The images will be labelled as "Research images, not for diagnostic use". Images will be emailed in an encrypted document to the parent/caregiver after the neuroradiologist review. Families can choose not to receive these images. Images will be sent to the parent/legal guardian in a password protected document through encrypted email or mail, as preferred by the parent/legal guardian.

10.3.7 Optional 6 month/12-month follow up

Participants who completed any number of sessions during the primary study a

10.4 Unanticipated Problems

An unanticipated problem (UP), as defined by the Department of Health and Human Services (DHHS) Office for Human Research Protection (OHRP), is any incident, experience, or outcome that meets all of the following criteria:

- The incidence, experience, or outcome is unexpected given the research procedures described in protocol-related documents (e.g., the study protocol, the informed consent documents) and the characteristics of the subject population being studied. An event may be considered unexpected if it exceeds the nature, severity, or frequency described in the study-related documents, Investigator's Drug Brochure, product labeling, or package insert.
- The incidence, experience, or outcome is related or probably related to participation in the research study. "Probably related" means the incidence, experience, or outcome is more likely than not to be caused by the research study procedures.
- The occurrence of the incidence, experience, or outcome suggests that the research places subjects or others at a greater risk of harm (physical, psychological, economic, or social) than was previously known or recognized.

The investigator will report UPs to the reviewing IRB and to the PI. The UP report will include the following information:

- Protocol identifying information: protocol title and number, PI's name, and the IRB project number;
- A detailed description of the event, incident, experience, or outcome;
- An explanation of the basis for determining that the event, incident, experience, or outcome represents an UP;
- A description of any changes to the protocol, informed consent documents, or other corrective actions that have been taken or are proposed in response to the UP.

10.5 Unanticipated Adverse Device Effect

An unanticipated adverse device effect means any serious adverse effect on health or safety or any life-threatening problem or death caused by, or associated with, a device, if that effect, problem, or death was not previously identified in nature, severity, or degree of incidence in the investigational plan or application (including a supplementary plan or application), or any other unanticipated serious problem associated with a device that relates to the rights, safety, or welfare of subjects.

An investigator shall submit to the sponsor and to the reviewing Institutional Review Board (IRB) a report of any unanticipated adverse device effect occurring during an investigation as soon as possible, but in no event later than 10 working days after the investigator first learns of the effect.

10.6 Protocol Deviations

Refer to section 11.5.

Any planned protocol deviations will be submitted to the sponsor, the FDA and the IRB before implementation when applicable. If an unplanned deviation occurs in case of emergency to protect the life or physical well-being of the participant, it will be reported no later than 5 working days.

10.7 Incidental Findings

N/A

10.8 Safety Oversight

The full details of the planned study monitoring are included in the Data Safety and Monitoring Plan (DSMP).

The PI will oversee the safety of the entire study, including careful assessment and appropriate reporting of all AEs and SAEs. A trained study team member will be present during stimulation to monitor the safety of the participant. The parent/legal guardian or adult participant and study team will report any adverse events, which arise after any session of tDCS or behavioral assessment, to the investigator and the investigator will convey the concerns to the Medical Monitor immediately upon receipt of this information to determine the optimal recommendation for care. The Medical Monitor will review each case after independent analysis of vital signs/symptoms and the occurrence of any minor or SAE. Incorporation of this Medical Monitor review will occur in addition to the safety and risk mitigation plans that we have established during each active session with the child and family. The Medical Monitor will review these reports and determine continuation of study based on comparative analysis of study stopping rules.

The Medical Monitor for this study is:

[name]
Assistant Professor (CHS), Department of Pediatrics
[name]
[contact]

[name] holds board certifications in General Pediatrics, Physical Medicine and Rehabilitation, and Pediatric Rehabilitation Medicine. [name] will utilize this background and her experience evaluating patients with cerebral palsy as the Waisman Center Cerebral Palsy Clinic Director to fulfill the role of Medical Monitor.

10.9 Study Monitoring

We have contracted with the UW Institute for Clinical and Translational Research (ICTR) Study Monitoring Service (SMS) for the proposed study to provide ongoing monitoring services to conduct and follow-up of monitoring visits throughout the life cycle of the study. The purpose of the SMS Program is to provide independent, ongoing monitoring to support compliance with good clinical practice (GCP) guidelines, federal, state and institutional regulations, policies, and guidance. The primary role of the SMS is to validate the integrity of the data collected and to assess compliance with the IRB approved protocol and applicable regulatory requirements, while ensuring the rights, safety and welfare of subject are protected.

For this study, SMS personnel will conduct a Site Initiation Visit (SIV) and ongoing Interim Monitoring Visits (IMVs), either on-site, remotely, centrally or a combination thereof, throughout the duration of the study. During IMVs, the monitors will review study materials, including but not limited to: regulatory files, consent forms, and drug accountability logs. SMS will review FDA communications to ensure compliance with applicable FDA IDE and regulations, guidelines, and institutional policies. SMS personnel will conduct a Close-Out Visit (COV) upon completion of the study at the study site.

Monitoring will consist of all (100%) consent and screening documents for each enrolled subjects along with all (100%) study-related records for a minimum of 20% of subjects enrolled. SMS personnel could increase the percentage of study or subject records to be reviewed if warranted by the ongoing monitoring findings, resulting in a partial or full review of up to 100% of the study-related subject records. In addition, the SMS staff will verify adherence to protocol eligibility criteria, verify documentation for the accountability and administration of the study product, verify documentation of study procedures, and verify that FDA required SAE reports were appropriately submitted.

10.10 Study Stopping Rules

Both Individual and Entire Study stopping rules are described below:

Death. Study stopped for both individual and entire study. A full investigation of event will be explored by entire study team. The medical monitor will review all details. Report of event will be distributed to all governing and monitoring committees.

Seizure: Individual- Immediate suspension of tDCS application for this particular child and initiation and follow-through of safe and effective seizure management. Refer to seizure management outline. Provide physician letter to subject which describes the research-related adverse event with physician interpretation.

Pregnancy: If at any time during the study, the participant states that they are pregnant, the participation will not be allowed to continue within the primary study. They will be allowed to participate in the 6 and 12-month follow up visits as described in 14.6 Reporting of Pregnancy.

Transient Decline in Motor Function (Individual). Immediate suspension of TMS intervention for the particular participant and initiation of assessment of the change. A written report with detailed documentation of decline in function will be submitted to the Medical Monitor. The participant's pediatrician and neurologist will also be contacted. Follow-up testing will then occur one week after suspension of the study to track progress and change in status with physicians contacted with results directly thereafter.

Transient Decline in Motor Function (Entire Trial). If any participant shows a decrease in function following any component of the proposed study (tDCS or behavioral assessment), the study will be stopped at that time for review by the Medical Monitor. If the Medical Monitor deems that the change in function does not indicate need for termination of the study, the study will recommence. If the Medical Monitor deems that the protocol has indications for change, the study will be reviewed by the investigative team, including consultants and will be changed and submitted for re-approval by the IRB before recommencing the study.

Entire Study- If another subject incurs a seizure proceed with steps for Individual Stopping Rules as noted above. Study will be suspended at this point and a thorough review by research team, medical monitor and consultants will occur in order to assess the need for amendment of the protocol or full stop/termination of study for future safety concerns.

Study Medical Director Evaluation. Recommend further evaluation to the participant and legal guardian by a neurologist if not the pediatrician\physician routinely involved in the participant's care. An identification of causality and re-evaluation of treatment design will occur by study researchers, including consultants, medical monitor and physicians in order to proceed. All procedures will be assessed for strict adherence to all intervention steps listed in the protocol. If deviation is found, error will be corrected. Proceed with study.

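### Section 10.10 states no hold on other children's active sessions after a first seizure, although a decrease in function in one participant stops the whole study for review

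*Combined protocol and SAP*

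**What the plan says.** Section 10.10 (Study Stopping Rules) covers both individual and study-level stopping.

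- **Death:** "Death. Study stopped for both individual and entire study".
- **Decrease in function, any one participant:** "the study will be stopped at that time for review by the Medical Monitor". The halt is reversible: "If the Medical Monitor deems that the change in function does not indicate need for termination of the study, the study will recommence".
- **First seizure:** "Immediate suspension of tDCS application for this particular child", with seizure management (by reference to a separate outline) and a physician letter.
- **Second seizure:** "If another subject incurs a seizure proceed with steps for Individual Stopping Rules as noted above. Study will be suspended at this point", followed by a review that may lead to amendment or termination.

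The last paragraph of 10.10, on evaluation by the Study Medical Director, adds: "An identification of causality and re-evaluation of treatment design will occur by study researchers, including consultants, medical monitor and physicians in order to proceed". It does not say which event sets this in motion, orders no suspension, and ends with an instruction to carry on with the study.

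Section 10.8 (Safety Oversight) sends adverse events to the Medical Monitor at once and states: "The Medical Monitor will review these reports and determine continuation of study based on comparative analysis of study stopping rules".

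**The concern.** Followed as written, a fall in one child's motor function, under a heading that calls it transient, halts everyone until the Medical Monitor has looked at it. A seizure in one child explicitly halts only that child. The event that most would regard as more serious has the looser study-level trigger, and the plan gives no reason for this.

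The plan itself treats seizure as a key risk. Section 8.1 excludes epilepsy and any seizure in the two preceding years, and section 10.2.7.1 has the follow-up record review look for new-onset seizures. Safety and tolerability form the primary objective, and section 6.1 hypothesises no serious adverse effects. If two children's courses fall close together, the second could receive active sessions before anyone has judged whether stimulation caused the first child's seizure.

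**Working it through.** The documents give no seizure risk, no review time and no operating characteristics for the stopping rules, so there is no stated figure to reproduce. The check has a textual part and an illustrative part.

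**1. The rules side by side**

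| Event in one participant | Explicit effect on that participant | Explicit effect on the others |
|---|---|---|
| Death | stopped | study stopped |
| Decrease in function | suspended, retested at one week | study stopped for review, may restart |
| First seizure | tDCS suspended | none stated |
| Seizure in a second participant | tDCS suspended | study suspended for review |

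Section 10.8 requires review of each event but ties continuation to these same rules. Sections 10.4 and 10.5 (unanticipated problems and device effects) require reporting, with corrective actions described in the former; neither imposes a pause.

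**2. Would another child be in an active session during the review?**

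Inputs from the documents: 10 participants; five consecutive days each, with active sessions on days 3 to 5 (section 7.1); enrolment and follow-up over 10 months (section 3.1), taken as 304 days; alternatively, 12 months of recruitment (section 8.5), taken as 365 days. Assumptions: start days independent and uniform; seizure on a random active day; review lasting W days. W = 7 is borrowed from the motor-decline rule ("Follow-up testing will then occur one week after suspension of the study to track progress").

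Another child's three active days meet a W-day window if they begin on any of W + 2 days. Ignoring edge effects, the chance that at least one of the other nine overlaps is 1 − (1 − (W + 2)/304)^9.

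| W (days) | Formula | Simulation (400,000 runs) |
|---|---|---|
| 1 | 0.085 | 0.086 |
| 7 | 1 − (1 − 9/304)^9 = 0.237 | 0.237 |
| 14 | 0.385 | 0.379 |
| 30 | 0.633 | 0.609 |

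Over 365 days with W = 7: 1 − (1 − 9/365)^9 = 0.201. With starts evenly spaced about 30 days apart, the next child's first active day falls at least 30 − 2 = 28 days after the seizure, so overlap is 0 for any review up to 14 days.

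**3. Unconditional size**

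The figures in step 2 presuppose a seizure. To remove that condition, multiply by P(at least one seizure among 10) = 1 − (1 − p)^10, with p assumed. The product is approximate, since it treats overlap as independent of how many seizures occur.

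| Assumed p | P(at least one) | × 0.237 (W = 7) |
|---|---|---|
| 1% | 0.0956 | 2.3% |
| 2% | 0.1829 | 4.3% |
| 5% | 0.4013 | 9.5% |

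A 1-day review at p = 1% gives 0.0956 × 0.086 = 0.8%.

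**4. How often a seizure leads to the explicit study suspension**

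Among trials with at least one seizure, the share with exactly one, where the two-subject trigger is never reached, is 10p(1 − p)^9 / (1 − (1 − p)^10). This is 95.5%, 91.2% and 78.5% at p = 1%, 2% and 5%. With 10 participants, the written seizure rule will therefore seldom act on the study as a whole.

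**The case against.** The strongest reply is that the closing paragraph of 10.10 already is the gate. It calls for a causality finding and a look at the treatment design before proceeding, and its neurologist referral fits a seizure. Motor decline and a second seizure have their own review paths, so a first seizure is its most natural subject. That reading is plausible and cannot be excluded. It remains an inference: the paragraph names no trigger and orders no hold, and it does not say what happens if procedures were followed correctly and stimulation is still suspected.

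A reader might also infer that a first seizure goes without study-level review, or that the trial has no pause anywhere. The documents support neither. Section 10.8 sends the event to the Medical Monitor immediately, and nothing there says the Monitor may act only once a rule has fired. Sections 10.4 and 10.5 would bring a qualifying event to the IRB. The Data Safety and Monitoring Plan and the seizure management outline are cited but not supplied; sections 14.1 to 14.6 in the contents list are not in the visible text, and section 10.3.7 breaks off mid-sentence. A pause, or a rule spacing the starts, could be stated in any of these.

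Two further points stand. The 9% to 61% overlap figures presuppose a seizure and should not be read as the trial's risk. The shares in step 4 show how rarely two events occur among 10 children; they do not measure harm. Finally, nothing in the documents requires equal triggers, and an isolated seizure may be background, since one more than two years old does not by itself exclude a child. That argues for a short, reversible pause over a termination rule.

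**Conclusion.** The point holds as a gap in the explicit rules. In the visible text, a first seizure expressly suspends stimulation only in the affected child, and no rule holds other children's active sessions while it is reviewed, although one participant's decrease in function stops the study. It does not show that the trial lacks seizure oversight or that a pause is absent from documents not supplied.

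The practical size is small: about 2% to 10% for a 7-day review, and 0% with even spacing and reviews up to 14 days. The range rests on random starts over 304 days, seizures on active days and assumed per-child risks of 1% to 5%. The case for change rests on the inconsistency and the low cost of removing it. This is a cheap improvement, held with medium confidence because relevant documents are unseen.

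**What to change.** Add to section 10.10: *After a first seizure in any participant occurring once current has been delivered (session 2 onward) in the primary study, active tDCS sessions in all participants are paused until the Medical Monitor has promptly reviewed causality and decided on continuation.* Starting at session 2 leaves out seizures before any current, including those on the mock day.

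Keep the existing suspension and wider review at a second seizure. State that the Study Medical Director paragraph applies to a first seizure, and make its closing instruction to continue conditional on the outcome of the review. If the Data Safety and Monitoring Plan or the seizure management outline already contains this pause, a citation in 10.10 is enough.

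The cost is one sentence, one clarification and a possible short pause in a 10-participant study. The safety monitor brings the active device to each session and takes it away afterwards (section 5.2), so a hold needs no device retrieval. The mechanism copies a reversible halt the sponsor already accepts for motor decline.
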